**A nomogram model to predict central lymph node metastasis in
thyroid papillary carcinoma suitable for primary hospitals**

Date updated: December 6, 2021

Study Protocol and Statistical Analysis Plan

Collection of Patients

1000 Patients who underwent total thyroidectomy or lobectomy and were diagnosed as PTC by pathological examination between June 2014 and September 2019 in Sun Yat-sen Memorial Hospital (Guangzhou, South China) and 200 patients in the First Affiliated Hospital of Zhengzhou University (Zhengzhou, North China) from March 2019 to November 2020 were selected as the subjects to construct the nomogram. The inclusion criteria were as follow: (1) underwent TC operation for the first time; (2) confirmed as PTC by postoperative pathological examination; (3) underwent ipsilateral or bilateral CLND. The exclusion criteria included: (1) complicated with other subtypes of TC or thyroid metastatic cancer; (2) received preoperative interventional therapy (such as radiofrequency and microwave therapy) or head and neck radiotherapy. the patient recruitment process was showed in Figure1. We randomized them at 7:3 and divided it into a training set and a verification set. Besides, 200 cases that met the inclusion and exclusion criteria above-mentioned in the First affiliated Hospital of Zhengzhou University were enrolled as a external verification set.

[figure not shown]

Fig 1. the recruitment process of patients in our study

Surgical Quality Control

All surgeries were conducted by at least two experienced surgeons. According to the preoperative US, all patients in our study underwent total thyroidectomy or lobectomy plus ipsilateral or bilateral CLND and then all specimens were for paraffin fixation and histological analysis in the department of pathology.

Baseline Characteristics

The following clinical features for each patient were obtained before surgery: gender, age, occupation, complicated with autoimmune diseases (absent / present), history of radiation exposure (absent / present), family history of thyroid cancer (absent / present), with other tumors (absent / present) and preoperative laboratory examinations including neutrophil count, lymphocyte count, platelet count, thyroid-stimulating hormone (TSH), free triiodothyronine (fT3), free thyroxine (fT4), anti-thyroglobulin antibody (TgAb), thyroid peroxidase antibody (TPOAb).

Preoperative US signatures of thyroid tumors were also included: distribution (unilateral / bilateral), shape (regular / irregular), maximum diameter, number (single / multiple), boundary (clear / semiclear / unclear), component (solid /cystic-solid), calcification (absent / microcalcification / macrocalcification), blood flow (absent / internal / annular), cervical lymph node enlargement (absent / present).

Statistical Analysis

Statistical analyses were performed using the Statistical Package for the Social Sciences (SPSS) for Windows, Version 25.0 and RStudio software. All tests were two-tailed, and a two-sided value of $P<0.05$ was considered statistically significant. The continuous variables for normally distributed data are presented as the mean \pm standard deviation (SD) and were compared by using the Student's t-test. For the variables with a skewed distribution, data are presented as medians (interquartile ranges). The categorical variables are reported as frequencies (percentages), and the characteristics of the patients were compared by using the chi-square test. A least absolute shrinkage and selection operator (LASSO) regression analysis conducted by using the glmnet R package was applied to identify the important preoperative predictors associated with CLNM in the training set, with the optimal values of the penalty parameter λ determined via 10-fold cross-validation. Multivariate logistic regression analysis were conducted to determine the potential nonlinear association between predictors and the risk of CLNM. Odd ratios (ORs), 95% confidence interval (CI) and probability values were obtained by logistic regression analysis. The area under the receiver operating characteristic (ROC) curve (AUC) was calculated to evaluate the accuracy of the nomogram for predicting CLNM. The calibration curve and Hosmer-Lemeshow tests were performed to evaluate the calibration of the nomogram. The decision curve analysis (DCA) was applied to validate clinical utility of the nomogram.

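### The Zhengzhou patients are given two incompatible roles, building the nomogram and testing it externally, and the 7:3 split names no hospital

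*Combined protocol and SAP*

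**What the plan says.** All the relevant text on set membership is in the Collection of Patients section of the combined protocol and SAP.

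- The opening sentence starts with "1000 Patients who underwent total thyroidectomy or lobectomy and were diagnosed as PTC by pathological examination between June 2014 and September 2019" at the Guangzhou hospital, adds "and 200 patients in the First Affiliated Hospital of Zhengzhou University (Zhengzhou, North China", and closes by saying that these patients, the Zhengzhou group dating "from March 2019 to November 2020 were selected as the subjects to construct the nomogram". Grammatically, both hospitals supply the construction subjects.
- After the eligibility criteria, and a note that "the patient recruitment process was showed in Figure1", comes the split: "We randomized them at 7:3 and divided it into a training set and a verification set". It names no hospital and gives no count.
- The last sentence reads "Besides, 200 cases that met the inclusion and exclusion criteria above-mentioned" and continues "in the First affiliated Hospital of Zhengzhou University were enrolled as a external verification set". It gives no dates.

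The Statistical Analysis section says that LASSO is "applied to identify the important preoperative predictors associated with CLNM in the training set". It does not say which hospital supplies that set or how large it is.

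**The concern.** The Zhengzhou cases are the plan's only test outside the centre where the model is developed. For that test to mean what its label says, no Zhengzhou record may influence predictor selection, the choice of λ or the coefficients. The opening sentence puts these patients on the construction side, the closing sentence puts them on the testing side, and the sentence between them does not say whom the split covers.

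An analyst who followed the text literally would randomise the pooled 1200. The model would then be tested partly on patients it had been fitted to, or at least in a hospital it had been trained on. Patient reuse inflates apparent performance, and the confidence interval around the external AUC would not reveal it. The document is written in the past tense, so the split may already have been run.

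**Working it through.** The visible text gives no set sizes and no sample-size calculation, so there is no figure of the plan's own to reproduce first.

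**Inputs from the document:** 1000 Guangzhou patients, 200 Zhengzhou patients (mentioned twice), split ratio 7:3.

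**Step 1: three readings of the split.**

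| Reading | Training | Internal verification | External | Zhengzhou patients in training |
|---|---|---|---|---|
| A. Guangzhou only | 0.7 × 1000 = 700 | 0.3 × 1000 = 300 | 200 | 0 |
| B. Pooled; the external 200 are the same people | 0.7 × 1200 = 840 | 0.3 × 1200 = 360 | the same 200 | about 140, all from the external set |
| C. Pooled; the external 200 are different people | 840 | 360 | another 200 (1000 + 200 + 200 = 1400 in all) | about 140, none from the external set |

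Reading A assumes that all 1000 are split.

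**Step 2: overlap under the pooled split.** The number of Zhengzhou patients drawn into training is hypergeometric (1200 patients, 200 from Zhengzhou, 840 drawn).

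- Mean = 840 × 200/1200 = 140.
- SD = √[840 × (200/1200) × (1000/1200) × (360/1199)] = 5.9.
- 95% range: 128 to 151. The chance that none is drawn is effectively zero (about 5 × 10⁻¹²⁸).
- Share of the training set: 140/840 = 16.7% (128/840 = 15.2% to 151/840 = 18.0%).
- Left out of training: 200 − 140 = 60 (200 − 151 = 49 to 200 − 128 = 72).

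**Step 3: what reuse could do to the external AUC (reading B).** This cannot be derived from the documents, so every model input here is assumed: 24 independent standard normal predictors (the plan lists 7 clinical, 8 laboratory and 9 ultrasound variables), 8 of them with coefficients of 0.2 to 0.5 per SD, identical effects in both hospitals, and CLNM in 30%, 40% or 50% of patients. The gap is the AUC on the 200 from the pooled-split model minus that from the Guangzhou-only model.

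| Simulated fit | Gap in external AUC |
|---|---|
| LASSO with 10-fold cross-validation, then logistic refit | 0.0271, 0.0245, 0.0235 at 30%, 40%, 50% CLNM |
| Plain logistic, all 24 predictors kept | 0.025 to 0.029 |
| Plain logistic, only the 8 true predictors | 0.007 to 0.008 |
| Plain logistic, all 24 kept, weaker effects | 0.032 to 0.035 |

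In the LASSO row the AUCs themselves were 0.7295, 0.7308 and 0.7227 (Guangzhou only) against 0.7567, 0.7552 and 0.7462 (pooled). The part due to reuse, net of each model's AUC in fresh patients, was 0.0249, 0.0213 and 0.0206. The remainder, 0.0271 − 0.0249 = 0.0022, 0.0245 − 0.0213 = 0.0032 and 0.0235 − 0.0206 = 0.0029, is real improvement from training on 840 instead of 700.

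For scale, the Hanley-McNeil standard error of an AUC of 0.73 in 200 patients is 0.0412, 0.0374 and 0.0355 at the three prevalences. The LASSO-row gap is therefore about 0.66 of a standard error in each case.

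**Step 4: reading C.** No external patient is reused. With equal effects in both hospitals, only the real gain of about 0.003 remains, and that is not bias. What is lost is the claim of testing in a centre the model has not seen.

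**The case against.** The best defence is that the section has one coherent meaning when read as a whole. The opening sentence introduces the study population, with construction loosely covering development and verification together. The split then yields the training and internal sets, and *Besides* adds Zhengzhou as a separate group. Under a pooled split *external* would be false and *Besides* pointless, while reading C needs a second group of exactly 200 that no sentence introduces. Figure 1 is the natural place for set membership and counts, and its absence here is not a fault of the plan.

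Most of this stands as evidence of intent: a Guangzhou-only split is the likely meaning. It does not repair the text. The construction sentence still includes Zhengzhou, no visible sentence says who is in the training set, and a figure showing three clean sets would leave that sentence wrong.

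Three stronger readings are tempting and unsupported:

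- A reader might infer that the external validation is contaminated. Nothing in the documents shows that Zhengzhou records entered the split.
- A reader might infer that the external results would be optimistic whichever 200 patients are meant. Optimism through reuse needs the same people; under reading C it would need differences between hospitals, on which the documents give nothing.
- A reader might take a shift of about 0.025 in AUC as the size of the bias. That figure comes from one set of assumptions. The gap depends on how many predictors survive selection and how strong they are, and the simulated independent normal predictors do not resemble the plan's many categorical variables.

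**Conclusion.** The inconsistency is real and should be corrected. As written, the section assigns the Zhengzhou patients both to model construction and to external verification. A literal pooled split would place about 140 of 200 (128 to 151) in training and spoil the plan's only out-of-centre test. That count rests only on the document's figures and on simple random allocation.

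The consequence is conditional. If the two mentions of 200 are the same people, which the matching number and hospital suggest but the missing dates leave open, the external AUC, calibration and decision curve would be optimistic. The AUC effect was roughly 0.007 to 0.035 under the assumed inputs, including about 0.003 of real gain. No size is claimed for calibration or the decision curve, or where effects differ between hospitals. This is a fault in the wording with a possible analytic consequence, not evidence that the analysis went wrong.

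**What to change.** - Take the Zhengzhou patients out of the sentence on constructing the nomogram.
- State that only Guangzhou patients are randomised 7:3 into training and internal verification sets, with the count in each (700/300 if all 1000 are split; the sponsor to confirm).
- State whether the two mentions of 200 Zhengzhou patients are the same people.
- State that Zhengzhou patients enter no predictor selection, λ tuning or coefficient fitting, and are scored only with the frozen nomogram.
- Check the analysis code once, and refit only if Zhengzhou records were in the split.

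The cost is a few sentences and one code check. If a refit proves necessary, the training set shrinks (700 instead of 840 if all 1000 are split), the coefficients become somewhat less precise, and the external AUC may fall.

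### No optimism correction or shrinkage is planned for the nomogram, and the 7:3 split is a valid but imprecise internal check: a cheap improvement, not an error

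*Combined protocol and SAP*

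**What the plan says.** *Collection of Patients* describes a Guangzhou cohort ("1000 Patients who underwent total thyroidectomy or lobectomy and were diagnosed as PTC by pathological examination") and 200 patients from Zhengzhou. The split sentence reads "We randomized them at 7:3 and divided it into a training set and a verification set". The Zhengzhou patients "were enrolled as a external verification set". An opening sentence, however, joins both hospitals' patients and says that they "were selected as the subjects to construct the nomogram".

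*Statistical Analysis* says that LASSO "was applied to identify the important preoperative predictors associated with CLNM in the training set", with 10-fold cross-validation used to choose λ. The next step is given as "Multivariate logistic regression analysis were conducted to determine the potential nonlinear association between predictors and the risk of CLNM", and it yields odds ratios, confidence intervals and P values. Performance is assessed by AUC and by two further steps: "The calibration curve and Hosmer-Lemeshow tests were performed to evaluate the calibration of the nomogram" and "The decision curve analysis (DCA) was applied to validate clinical utility of the nomogram".

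The text does not state the set sizes, the reason for the split, the rule for picking λ from the cross-validation, or which coefficients the nomogram is drawn from. It mentions no bootstrap, optimism correction, shrinkage of the logistic fit, calibration slope or calibration intercept.

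**The concern.** Two separate matters are involved.

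**Calibration of the nomogram.** LASSO shrinks coefficients while it selects. If the selected predictors are then refitted by ordinary logistic regression, that shrinkage is lost and the coefficients tend to be too large. High predicted risks are then too high and low ones too low. A nomogram is read as an individual's probability, and the planned decision curve depends on those probabilities, so this matters even when the AUC hardly moves.

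**Use of the data.** A random split within one hospital and period checks the model in the population it was built from. Zhengzhou already supplies independent patients. About 30% of the development data therefore go to a question that resampling answers more precisely.

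**Working it through.** The plan states no sample-size calculation, event rate or target AUC, so it has no figure of its own to reproduce.

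**1. Set sizes.** 0.7 × 1000 = 700 and 0.3 × 1000 = 300. Applied literally to all 1200 patients, the ratio would give 840 and 360. The separate external set makes 700/300 the coherent reading.

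**2. Candidate parameters.** *Baseline Characteristics* lists 7 clinical and 8 laboratory variables, counted as 15 parameters with occupation as one (more if it has over two categories). The ultrasound list has 9 variables: six with one parameter each and three with three levels, so 6 + 3 × 2 = 12. Total 15 + 12 = 27. Nonlinear terms would add to this.

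**3. Expected shrinkage S of an unpenalised model.** Solve n = P / [(S − 1) ln(1 − R²cs/S)] with P = 27. Example, assuming prevalence 0.4 and Nagelkerke R² 0.25:
- The maximum R²cs is 1 − (0.4^0.4 × 0.6^0.6)² = 0.740, so R²cs = 0.25 × 0.740 = 0.185.
- At n=700, S = 0.844. Check: 27 / [(−0.156) × ln(1 − 0.185/0.844)] ≈ 700.
- At n=1000, S = 0.885.

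Over prevalence 0.3–0.5 and Nagelkerke R² 0.15–0.35 (all assumed):

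| n | S |
|---|---|
| 700 | 0.747–0.890 |
| 840 | 0.780–0.906 |
| 1000 | 0.808–0.920 |

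**4. Simulated calibration slope.** Assumptions: 27 predictors, 11 true effects, latent correlation 0.2, prevalence 0.4, 200 cohorts per AUC, performance measured in 20,000 new patients.

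| LASSO then unpenalised refit | n=700 | n=1000 |
|---|---|---|
| AUC 0.70, minimum-error λ | 0.757 | 0.814 |
| AUC 0.70, one-SE λ | 0.815 | 0.855 |
| AUC 0.78, minimum-error λ | 0.843 | 0.886 |
| AUC 0.78, one-SE λ | 0.884 | 0.920 |

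The larger sample alone closes 22–31% of the gap to 1; for example (0.920 − 0.884)/(1 − 0.884) = 31%. Keeping the LASSO coefficients at n=700 gives slopes of 1.04–1.07 (minimum-error λ) or 1.44–1.64 (one-SE λ), which is the opposite direction.

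**5. Which change does the work.** A second simulation with a different assumed effect pattern (56–64 cohorts per cell, 15 full-process resamples each) compared the options directly:

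| Option | Mean slope | RMSE from 1 |
|---|---|---|
| 700, bootstrap shrinkage | 1.00–1.02 | 0.10–0.13 |
| 1000, no shrinkage | 0.86–0.90 | 0.13–0.16 |
| 1000, bootstrap shrinkage | – | 0.085–0.11 |

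Shrinkage within the existing split corrects the mean slope. Dropping the split as well lowers the RMSE by only about 0.015–0.02.

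**6. Precision of the internal AUC.** Hanley–McNeil variance: [A(1−A) + (n₁−1)(Q₁−A²) + (n₀−1)(Q₂−A²)] / (n₁n₀), with Q₁ = A/(2−A) and Q₂ = 2A²/(1+A). Example with A = 0.75, n = 300 and prevalence 0.4 (n₁ = 120, n₀ = 180):
- Q₁ = 0.600, Q₂ = 0.643, A² = 0.5625.
- Variance = (0.1875 + 119 × 0.0375 + 179 × 0.0804)/21,600 = 0.00088.
- SE = 0.0297 and half-width = 1.96 × 0.0297 = 0.058.

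Over AUC 0.70–0.80 and prevalence 0.3–0.5, the half-width is 0.050–0.068 at n=300 (0.046–0.062 at n=360) and 0.027–0.037 at n=1000. The optimism-shifted bootstrap interval had a simulated half-width of 0.028–0.033.

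**7. Error of the internal estimates** (114 cohorts per AUC, 100 full-process resamples each), as RMSE:

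| Quantity | Hold-out of 300 | Bootstrap on 1000 |
|---|---|---|
| AUC | 0.029–0.033 | 0.014–0.019 |
| Calibration slope | 0.12–0.17 | 0.06–0.10 |
| Net benefit, thresholds 0.3 and 0.5 | 0.030–0.034 | 0.017–0.020 |

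The model's true AUC rises by 0.004–0.009 when 1000 rather than 700 patients are used.

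**8. The planned calibration test.** At a true slope of 0.8, simulated Hosmer–Lemeshow power is 11–25% at n=200 and 14–32% at n=300. A non-significant result would say little.

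**The case against.** A random hold-out plus a geographically separate set is a legitimate design. The hold-out needs no optimism correction, and in simulation it was nearly unbiased (mean AUC error +0.003). That stands: no planned result is invalid, and what the split costs is mainly precision.

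A reader might infer that the split makes the nomogram miscalibrated, or that pooling all 1000 patients would cure it. Neither the plan nor the figures support this. Most of any overfitting would come from an unpenalised refit, and shrinkage repairs the mean slope with the split kept.

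The harm to calibration is also conditional. *Statistical Analysis* does not say that the nomogram uses refitted coefficients; if it keeps the LASSO coefficients, predictions would if anything be too moderate.

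A bootstrap that repeats only the λ choice, LASSO and refit may also fall short. The logistic step is described as examining nonlinear association and yields P values, with 0.05 as the significance level. If either shapes the model, it must be repeated too. In a check with a P-value filter, leaving the filter out of the bootstrap left the mean slope at 0.89–0.93 after shrinkage.

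Finally, the simulations cover few effect patterns, so their ranges understate the uncertainty. The shifted AUC interval covered 91–100% across settings, so it is approximate.

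**Conclusion.** The point holds as a cheap improvement worth making, with medium confidence.

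- **Calibration:** the absence of optimism correction and shrinkage matters if the nomogram uses an unpenalised refit. Predicted risks would then be somewhat too extreme, by the shrinkage factors in step 3. Shrinkage is the main remedy, and it does not depend on dropping the split.
- **Split:** valid but inefficient. Internal AUC, slope and net benefit are estimated with about 1.6 to 2 times the error achievable from the same patients. Discrimination hardly changes.

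The sizes rest on assumptions outside the documents: the refit, 27 parameters, prevalence, AUC or R², and the effect pattern. A reader might also infer from the opening sentence of *Collection of Patients* that Zhengzhou patients help to build the model. The later assignment of those patients to external verification points the other way, and Figure 1 is not available here to confirm it, so this calls for clearer wording and is not a demonstrated leak.

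**What to change.** 1. State the λ rule, whether nonlinear terms or P values affect the model, and which coefficients the nomogram uses.
2. Develop on all 1000 Guangzhou patients. Validate internally with at least 500 bootstrap resamples that repeat every data-driven step: λ choice, LASSO selection, any nonlinear terms, any P-value filtering, and the refit.
3. Report optimism-corrected AUC (95% CI: the apparent-AUC interval shifted by the estimated optimism), calibration slope, calibration curve and decision curve.
4. If coefficients are refitted, multiply them by the corrected slope and re-estimate the intercept before drawing the nomogram.
5. If the sponsor keeps the split, apply the same bootstrap shrinkage within the 700.
6. In either case, state that the 200 Zhengzhou patients take no part in model building. Report AUC, calibration intercept and calibration slope there with 95% CIs, beside the planned calibration curve, without relying on the Hosmer–Lemeshow P value. With 200 patients the slope half-width is about 0.25–0.37 at a true slope of 0.8, so this is an estimate with an interval and not a precise one.

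**Cost:** computing time and SAP wording; no new patients. Dropping the split loses the separate internal verification panel. Reported figures may look slightly less favourable. Shrinkage corrects calibration on average, not in every data set.

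### On the natural reading, an unpenalised logistic refit after LASSO gives nomogram risks that are on average too extreme, and no planned step corrects this

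*Combined protocol and SAP*

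**What the plan says.** The Statistical Analysis section describes two modelling steps. LASSO "was applied to identify the important preoperative predictors associated with CLNM in the training set". Its tuning is described only as "with the optimal values of the penalty parameter λ determined via 10-fold cross-validation". Multivariable logistic regression follows. Its stated purpose is to examine possible non-linear relations between predictors and risk, and the section adds: "Odd ratios (ORs), 95% confidence interval (CI) and probability values were obtained by logistic regression analysis". The significance rule is "a two-sided value of $P<0.05$ was considered statistically significant".

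On performance, the section says "The calibration curve and Hosmer-Lemeshow tests were performed to evaluate the calibration of the nomogram" and "The decision curve analysis (DCA) was applied to validate clinical utility of the nomogram".

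On data, Collection of Patients says "We randomized them at 7:3 and divided it into a training set and a verification set", and a further 200 patients from the second hospital form an external set.

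The documents do not state:
- whether λ is the minimum-error or the one-standard-error value;
- whether the nomogram takes its coefficients from LASSO or from the logistic model;
- in which patients the logistic model is fitted;
- in which set calibration is judged;
- any shrinkage, optimism correction or recalibration.

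**The concern.** LASSO selects and shrinks at once, and the shrinkage offsets the optimism that selection brings. The plan gives LASSO a selecting role, and ordinary logistic odds ratios with confidence intervals and P values are not penalised estimates. So the natural reading is an unpenalised refit of the survivors in the same training patients. Those predictors were kept because they looked strong in those patients, and the refit takes their apparent strength at face value. High risks then come out too high and low risks too low.

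The title offers a tool for "thyroid papillary carcinoma suitable for primary hospitals", where the printed probability would be read as the patient's risk. The same probabilities enter the decision curve.

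**Working it through.** The plan states no calibration slope, shrinkage factor or event count, so there is no planned figure to reproduce. The check is by simulation.

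**Inputs from the documents**
- Training size: 0.7 × 1000 = 700, leaving 300 for verification. If the split covers all 1200 patients, training is 0.7 × 1200 = 840.
- External set: 200.
- Candidate columns, if every listed variable enters and occupation counts as one: 7 clinical + 8 laboratory + 12 ultrasound (six with one column, three with two) = 27.

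**Assumptions not in the documents**
- Metastasis prevalence 30–50%; true AUC 0.65–0.80; 3 to 12 true predictors; linear terms only.
- A 15-column sensitivity case drops 12 noise columns.

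**Method.** LASSO logistic path, 10-fold cross-validation, unpenalised refit of the survivors, then the calibration slope β in 10,000 new patients from logit Pr(metastasis) = α + β × (predicted logit). β below 1 means risks are too extreme. There were 300 replicates per scenario (250 at n = 840).

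**Refit slope at minimum-error λ**

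| Scenario | Mean slope (share of runs below 1) |
|---|---|
| 27 columns, n = 700, 7 true predictors, 40% prevalence, AUC 0.65 / 0.70 / 0.75 / 0.80 | 0.68 (98%) / 0.76 (96%) / 0.81 (98%) / 0.84 (98%) |
| As above, AUC 0.70, prevalence 30% / 50% | 0.75 (98%) / 0.77 (99%) |
| As above, AUC 0.70, 3 / 12 true predictors | 0.81 (94%) / 0.73 (99%) |
| n = 840, AUC 0.65 / 0.70 / 0.80 | 0.70 / 0.78 / 0.87 |
| 15 columns, AUC 0.65 / 0.70 / 0.80 (the last with 3 true predictors) | 0.76 (97%) / 0.85 (95%) / 0.92 (82%) |

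Smaller runs with separately written code and independent predictors gave 0.64 / 0.74 / 0.86 at AUC 0.65 / 0.70 / 0.80 (40 replicates) and 0.67 / 0.76 / 0.82 / 0.86 at AUC 0.65 / 0.70 / 0.75 / 0.80 (60 replicates). Taken together, the range for 27 columns and n = 700 is about 0.64–0.86. A scenario with weak effects throughout gave 0.55. At the one-standard-error λ the refit slope was 0.77–0.94 in the main runs and 0.71 / 0.84 / 0.93 in a smaller one.

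**What a slope of 0.76 means.** At AUC 0.70 and 40% prevalence, the top tenth is predicted 75% against a true 68%, and the lowest tenth 12% against 17%. A hand check, shrinking about the mean logit ln(0.4/0.6) = −0.405:
- Top: ln(0.75/0.25) = 1.099; 0.76 × (1.099 + 0.405) − 0.405 = 0.738, a risk of 68%.
- Lowest: ln(0.12/0.88) = −1.992; 0.76 × (−1.992 + 0.405) − 0.405 = −1.611, a risk of 17%.

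Over all runs with 27 columns at minimum λ, 12–37% of new patients receive a risk at least 5 points from the calibrated value. With 15 columns it is 6–21%.

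**If LASSO's own coefficients are used.** The mean slope is 1.01–1.20 at minimum λ (slightly too moderate) and about 1.5–2.2 at one standard error (strongly too moderate).

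**Can the planned checks see it?** With 27 columns at minimum λ, Hosmer-Lemeshow rejects in 15–33% of 300-patient sets and 18–23% of 200-patient sets, and in 4–7% if run in the training set. A 95% interval for the slope lies wholly below 1 in 32–54% and 25–37% of the 300- and 200-patient sets. On a curve by tenths, the 7-point gap in the top tenth has standard error √(0.68 × 0.32/30) = 0.085 or √(0.68 × 0.32/20) = 0.104.

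**P values.** Among noise predictors that survive selection at minimum λ, 11–20% have P < 0.05 (27 columns, all runs). Over all null candidates, the share both selected and significant is 5–6%, against 4–6% in a full model. Interval coverage for selected true predictors is 94–97%.

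**The case against.** The strongest objection is that the refit is inferred. The plan does not say that the nomogram is built from the logistic model, and the direction reverses if it is not. This stands, and it is why the conclusion is conditional. It does not clear the plan, because of the LASSO-coefficient options only minimum-error λ comes near a slope of 1, and the plan does not commit to it.

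The plan also mentions possible non-linear associations, while the simulations use linear terms. This stands as a limit on the figures. Added terms would probably not remove overfitting, and they would have to be inside whatever procedure is corrected.

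This is ordinary overfitting, and selection is not its cause: a full model without selection had slopes of 0.62–0.82, slightly worse. The practical loss may also be small. In a 50-replicate run at AUC 0.70 and 40% prevalence, perfect recalibration added only 0.5–5 per 1000 patients to net benefit across thresholds 0.2–0.6. Both points stand, and they keep this an inexpensive improvement and not a fatal fault.

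Finally, two verification sets are planned, and performance measured in them is honest. That is correct, but measuring is not correcting, and the power is low. The simulated 200-patient set came from the same population as the training data. The real one is from another hospital and period, so its detection rates may differ.

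**Conclusion.** The point holds conditionally. If the survivors are refitted without penalty in the training set, nomogram risks for new patients are on average too extreme, by the slopes shown above. The effect is milder with fewer candidates or the one-standard-error λ, and worse with weaker signal. Single refits can still have a slope above 1. Size depends on the assumed prevalence, signal, number of candidates and linear terms; confidence is moderate.

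A reader might infer three stronger things that the documents do not support:
- **That the nomogram is bound to be overconfident.** The coefficient source is unstated, and with LASSO coefficients the error runs the other way.
- **That the odds ratios, intervals and P values are invalid.** Inflation is confined to noise predictors that survive selection; overall false positives stay near 5%, and coverage for selected true predictors is near nominal. No passage says that P < 0.05 decides what enters the nomogram. This is secondary.
- **That the reported validation would be biased.** Verification-set results would show the miscalibration fairly; they would simply leave it in place.

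**What to change.** 1. State the λ rule and the coefficient source. If the survivors are refitted, multiply their coefficients by a shrinkage factor from a bootstrap that repeats λ choice, selection, refit and any non-linear terms in every resample (copies of a patient kept in one cross-validation fold), and re-estimate the intercept. Alternatively, prespecify minimum-error λ and use the LASSO coefficients directly; do not do this at one standard error.
2. Report calibration slope and intercept with 95% intervals in both the 30% verification set and the 200-patient external set, beside the calibration curve. Do not rely on Hosmer-Lemeshow alone.
3. Label post-selection odds ratios, intervals and P values as descriptive.

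The bootstrap option was checked with 100 replicates of 60 resamples at each AUC. At minimum λ and AUC 0.65 / 0.70 / 0.75 / 0.80, the mean slope moved from 0.65 / 0.75 / 0.81 / 0.85 to 0.88 / 0.95 / 0.97 / 0.99. Patients at least 5 points off fell from 37 / 29 / 22 / 15% to 9 / 5 / 5 / 3%. Mean distance of the slope from 1 was 0.15–0.35 for the plain refit, 0.07–0.16 after bootstrap shrinkage and 0.13–0.19 with LASSO coefficients at minimum λ.

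The cost is some extra R code and a short edit to the plan, with no new data. Odds ratios move toward 1, P values lose confirmatory standing, and the correction is only partial when signal is weak (slope about 0.88 at AUC 0.65).
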